8.2.3.2. Planned Exploratory Safety Display Details

Blood Pressure

The last on-treatment BP parameter change from baseline value (SBP, DBP, and MAP) recorded prior to the first change in BP medications will be summarized using mean, standard deviation, minimum, P25, median, P75, and maximum by treatment group. The first change in blood pressure medication occurs at the earliest time a new anti-hypertensive medication is administered or if the dose or frequency of an existing blood pressure medication is changed for any reason (increased, decreased, discontinued, or switched to another agent) in any anti-hypertensive medication, except medication records with frequencies of "Once only" and "PRN."

Number of BP medications per subject while the subject was on treatment will be summarized using mean, standard deviation, minimum, P25, median, P75, and maximum for each scheduled visit by treatment group. Number of BP medications for each subject at baseline is defined as the number of medications taken on the day before randomized treatment start date. For end of treatment, it is defined as the number of medications taken on last non-zero dose date + 1 day. The number of BP medications at all other nominal visits is defined as the number of medications taken on the day of the visit. Medication records with frequencies of "Once only" and "PRN" will be excluded from this summary.

Change from baseline in the number of BP medications per subject while the subject was on treatment will be summarized using mean, standard deviation, minimum, P25, median, P75, and maximum for each scheduled visit by treatment group. The number of BP medications at baseline, end of treatment and all other nominal visits will be defined as described in the previous paragraph. Medication records with frequencies of "Once only" and "PRN" will be excluded from this summary.

Additionally, the number and percentage of subjects who had no change, at least one change, an increase, a decrease or a switch in the dosage or number of BP medications from baseline while the subject was on treatment will be summarized for each scheduled post-baseline visit by treatment group (see Section 10.6.4 for details of classifying BP medication changes). Medication records with frequencies of "Once only" and "PRN" will be excluded from this summary.

Cumulative number of changes in on-treatment BP medications from baseline to Week 52 and End of Treatment will be summarized by treatment group. For all records except with frequencies "Once only" and "PRN," the cumulative number of changes will be summarized using mean, standard deviation, minimum, P25, median, P75, and maximum. The number of percentage of subjects with no change and at least one medication change will be displayed excluding "Once only" and "PRN" records. For subjects with at least one change, the number and percentage of subjects for each reason (increase, decrease, and switch) will be displayed (see Section 10.6.4 for details of counting BP medication cumulative changes) by treatment group. Number and percentage of subjects for each reason of BP medication change will be displayed by treatment group. Cumulative number of changes in on-treatment BP medication from baseline to Week 52 and End of Treatment for "Once only" records only will be

summarized using mean, standard deviation, minimum, P25, median, P75, and maximum (see Section 10.6.4 for details of counting BP medication cumulative changes) by treatment group.

Number and percentage of subjects with at least one PRN record at baseline and ontreatment BP medication during the period from randomized treatment start date to Week 52 and End of Treatment will be displayed by treatment group.

Number and percentage of subjects with any BP medication taken at baseline (the day before randomized treatment start date) and any on-treatment BP medication during the period from randomized treatment start date to Week 52 and End of Treatment will be displayed by treatment group.

Lipid Parameters

Lipid parameter values for this study include total cholesterol, LDL-C (direct) and HDL-C. These values are collected according to the schedule outlined in the Time and Events table (see Section 10.2.1). Lipid parameter values follow the derivation guidelines for laboratory values outlined in Section 10.6.4. The summaries described below will include summaries in both SI units and conventional units for each of the lipid parameters and will summarize log-transformed values.

Total cholesterol, LDL-C (direct), and HDL-C on-treatment values will be logtransformed and summarized using geometric mean, CV, minimum, P25, median, P75, and maximum for each scheduled visit by treatment group.

Percent change from baseline in log-transformed total cholesterol, LDL-C (direct), and HDL-C on-treatment values will be summarized using geometric mean, 95% confidence interval, minimum, P25, median, P75, and maximum for each scheduled visit by treatment group.

8.2.4. Adverse Event Safety Analyses

Adverse events will be coded using the Medical Dictionary for Regulatory Activities (MedDRA) coding dictionary.

The reporting of the CEC-adjudicated CV endpoint events has been described in Section 7.2, Section 8.2.1, and Section 8.2.2. However, AE summaries and analysis will also include the AEs and SAEs associated with the adjudicated events listed below:

- All-cause mortality (CV and non-CV mortality)
- Non-fatal MI
- Non-fatal stroke
- Hospitalization for HF
- Thromboembolic events (vascular access thrombosis, deep vein thrombosis, pulmonary embolism)

200807 | Statistical Analysis Plan Amendment 3 03 Mar 2021 | TMF-11879471 | 2.0

CONFIDENTIAL

200807

For the purpose of AE summaries and analysis, the investigator-reported AE details will be used, regardless of the adjudication outcome of the event.

Adopting recommendations from the Pharmaceutical Research and Manufacturers of America (PhRMA) Safety Planning, Evaluation and Reporting Team (SPERT) [Crowe, 2009], the first two tiers of the three-tier system will be used for the evaluation of AEs to examine the level of statistical evidence for differences between treatment groups.

- Tier 1 events in this study are defined as treatment emergent AEs of special interest (AESI). Tier 1 events will include AEs which meet criteria for inclusion as an AESI (see Section 10.6.4). Statistical comparisons will be made to compare the number and % of AESIs between the treatment groups, using the CMH chi-square test. A nominal statistical association will be declared if the unadjusted two-sided p-value for an event is less than 0.05.
- Tier 2 events in this study are defined as the most common treatment emergent AEs (those occurring in ≥ 5% of subjects in any treatment group). Tier 2 events are mutually exclusive of the Tier 1 AESI events. Any statistical comparisons for Tier 2 events will be made to compare treatment groups with multiplicity adjustment, using a CMH chi-square test, and the double false discovery rate (FDR, see Section 10.6.4) [Mehrota, 2012]. The double FDR multiplicity procedure is designed to limit the number of false positive signals identified to no more than two-sided 10% (the false discovery rate).

Unless otherwise specified, all other AE and SAE summaries will include all AEs.

See Section 10.4.1 for AE treatment state definitions.

The adverse event safety analyses will be based on the Safety population, unless otherwise specified.

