7.2.2. Planned CV Safety (MACE) Co-Primary Statistical Analyses

CV	/ Safety (MACE) Co-Primary Statistical Analyses
	dpoint(s)
•	Time to first occurrence of adjudicated MACE
Мо	odel Specification
•	The Cox Proportional Hazards model will adjust for the following baseline categorical values: o Treatment
	 Dialysis type (as randomized, see Section 10.10.2)
	 Region (as randomized, see Section 10.9 & Section 10.10.2)
•	Confidence intervals for the rate per 100 person-years will also be reported. For within-group rates, the two-sided 95% CI will be obtained using an exact Poisson method. For difference in rates between treatments, the two-sided 95% CI will be constructed with a Normal approximation using Wald's method [Liu, 2006].
•	The co-primary analysis will use only adjudicated safety endpoints as determined by the clinical endpoint committee (CEC) within the time period for follow-up of CV endpoints defined in Section 10.6.4.
•	Calculation of time-to-event or censoring is described in further detail in Section 10.6.4.
•	First occurrence of adjudicated MACE for a subject is defined as the first adjudicated event, determined by the event date, that is indicated as all-cause mortality, non-fatal MI or non-fatal stroke with further details in Section 10.6.4.
Мо	odel Checking & Diagnostics
•	Refer to Appendix 12: Model Checking and Diagnostics for Statistical Analyses.
Мо	odel Results Presentation
•	A summary of the number and percentage of subjects having first-occurrence MACE will be provided by treatment group. The number and percentage of the types of events that make up the first occurrence of MACE will also be provided by treatment group.
•	A summary of all MACE including the number and percentage of subjects and number of events (including first and subsequent MACE) by type of event will be provided by treatment group. Subjects experiencing MACE will be further broken down into subjects who experienced

- group. Subjects experiencing MACE will be further broken down into subjects who experienced exactly one MACE, subjects who experienced exactly two MACE, and subjects who experienced more than two MACE. The number and percentage of subjects in each of these categories by event type combinations will be provided by treatment group.
- The hazard ratio, two-sided 95% CI, one-sided p-value for the statistical non-inferiority test,

200807

CV	Safety (MACE) Co-Primary Statistical Analyses

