- The models will include factors for treatment, time, prognostic randomization stratification factors (see Section 10.10.2), baseline BP parameter and the baseline BP parameter by time and treatment by time interaction terms. Analyses will be done with the MIXED procedure in SAS, using the Kenward-Roger option to estimate denominator degrees of freedom and standard errors. For analyses using on- and off-treatment values, subjects who withdraw from the study before Week 52 are considered to be missing at random and in the analysis using on-treatment values only, subjects who permanently discontinue randomized treatment before Week 52 are assumed to be missing at random.
- The difference in change from baseline in BP (SBP, DBP, and MAP) at the derived end of treatment (see Section 10.6.4) will be analyzed with an ANCOVA model including terms for treatment, prognostic randomization stratification factors (see Section 10.10.2) and the corresponding baseline BP parameter. This analysis will be performed using on-treatment BP values only.

200807

Sec	ondary Safety Statistical Analyses: Blood Pressure
•	The number of on-treatment BP exacerbation events per 100 patient years will be calculated (see Section 10.6.4). Confidence intervals for the rate per 100 patient years will also be reported. For within group rates and the ratio of model estimated exacerbation rates, the point estimates. two-sided 95% confidence intervals, and one-sided p-value for the treatment group comparison will be obtained using a negative binomial model with treatment and the prognostic randomization strata as covariates and the logarithm of time on-treatment as an offset variable.
Мо	del Results Presentation
	BP parameter values (SBP, DBP, and MAP) will be summarized using mean, standard deviation, minimum, P25, median, P75, and maximum at each visit by treatment group. In addition to scheduled visits, the derived baseline value and end of treatment values will be summarized (see Section 10.6.4). Summaries of on-treatment BP values only and on- and off-treatment BP values together will be produced. A summary of on-treatment BP values by baseline dialysis type will be produced. On-treatment BP parameter values will be plotted by visit using a line plot. BP parameter change from baseline values (SBP, DBP, and MAP) will be summarized using

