8.2.4.2. Planned Adverse Event Safety Statistical Analyses

AESIs & PhRMA SPERT Adverse Event Analyses

Adverse events of special interest are described in Section 10.6.4.

Summaries of AESIs will include the number, percentage and rate per 100 person-years of subjects having at least one occurrence, the number of events, the number of subjects by number of occurrence, the characteristics of the AE (serious, drug-related, etc.), outcome, maximum intensity, time to first onset/worsening, and action taken summarized by treatment group. For each count, a subject will be summarized as follows:

- Serious/drug-related/severe/fatal: If any specific AE falls in the respective category, the subject will be counted in that category.
- Outcome: The subject will be counted within a category if there is at least one specific AE in that category.
- Maximum intensity: The specific AE with the maximum intensity will be counted for this purpose. For example, a subject will be counted in the 'severe' category if there is at least one specific AE with severe intensity. A subject will be counted in the 'moderate' category if there is at least one specific AE with moderate intensity and there is no specific AE with severe intensity.
- Time to first onset/worsening (days): The earliest of onset dates for the specific AE treatment start + 1

If the AE onset date/AE worsening and/or resolution date is missing or incomplete in the database for any occurrence of the specific AE, time to first onset/worsening will be left missing for the subject. These summaries of special interest AEs will be provided for those AEs classified as treatment emergent.

Cumulative incidence function (CIF) plots may be produced for each AESI summarizing the time to first occurrence of the AESI by treatment group. If there are less than 20 subjects total for both the daprodustat and rhEPO arm, then these plots will not be created. Competing risks for the AESI cumulative incidence plots include:

AE of Special Interest (Event of interest)	Competing Risk Events
Thrombosis and/or tissue ischemia secondary	Death due to any cause prior to the AESI
to excessive erythropoiesis	
Cardiomyopathy	Death due to any cause prior to the AESI
Pulmonary artery hypertension	Death due to any cause prior to the AESI
Cancer-related mortality and tumor progression	All other non-cancer-related death prior to the
and recurrence	AESI (use death date as the competing risk
	date)

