Esophageal and gastric erosions	Death due to any cause prior to the AESI
Proliferative retinopathy, macular edema,	Death due to any cause prior to the AESI
choroidal neovascularization	
Exacerbation of rheumatoid arthritis	Death due to any cause prior to the AESI
Worsening of hypertension	Death due to any cause prior to the AESI

Additionally, as a part of the PhRMA SPERT analyses described in Section 8.2.4, treatment emergent AE of special interest are considered Tier 1 events. The relative risk, corresponding two-sided 95% confidence intervals and two-sided p-values comparing daprodustat vs. rhEPO for these Tier 1 AEs will be provided.

200807

The number, percentage and rate per 100 person-years for subjects reporting Tier 2 AEs will be summarized by system organ class, preferred term and treatment group. Additionally, as a part of the PhRMA SPERT analyses described in Section 8.2.4, the most common treatment emergent AEs that are not Tier 1 AEs are considered to be Tier 2 AEs. The relative risk will be calculated for these Tier 2 AEs and a corresponding two-sided 95% confidence interval comparing daprodustat vs. rhEPO. Two two-sided p-values will be displayed: one that makes no adjustment for multiplicity and one that makes the double FDR adjustment.

Dot plots displaying the incidence of the event will be provided for the Tier 1 and Tier 2 events by AESI term (Tier 1)/ preferred term (Tier 2) and treatment group. The incidence rate in each treatment group and corresponding two-sided 95% confidence interval for the relative risk of the daprodustat group compared to the rhEPO group will be provided.

Adverse Events

The number and percentage of subjects reporting at least one AE will be provided for each treatment group. These events will be summarized by treatment group, primary system organ class, and preferred term. Pre-treatment and treatment emergent AEs will be summarized separately.

The number and percentage of subjects and the number of occurrences of all treatment emergent AEs will be summarized by primary system organ class, and preferred term.

Summaries of all treatment emergent AEs will be produced for the age group, gender, race group, baseline dialysis type, weight quartile subgroups. Summaries of treatment emergent AEs by subgroup will be produced twice: by system organ class and preferred term and separately by overall frequency.

A listing of AE records for all subjects who reported AEs will be produced.

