Summaries of characteristics of COVID-19 AEs will include the number, percentage of subjects having at least one occurrence, the outcome, maximum intensity, and the duration of the AE summarized by treatment group. For each count, a subject will be summarized as follows:

- Outcome: The subject will be counted within a category if there is at least one specific AE in that category.
- Maximum intensity: The specific AE with the maximum intensity will be counted for this purpose. For example, a subject will be counted in the 'severe' category if there is at least one specific AE with severe intensity. A subject will be counted in the 'moderate' category if there is at least one specific AE with moderate intensity and there is no specific AE with severe intensity.
- Duration of the occurrence (days): AE resolution date AE onset date/AE worsening date + 1 for the occurrence

A summary of the number and percentage of subjects with COVID-19 symptoms will be produced.

A summary of exposure adjusted incidence rates over time (see Section 10.6.4) will be produced by treatment group for any treatment emergent AE, any treatment emergent SAE, and any treatment emergent Severe AE, for two periods – pre COVID-19 pandemic and during COVID-19 pandemic. The summary will be produced overall, by Country, Region, Sex, and by Age at randomization (Grouping 2) (see Section 10.10.1). A summary of exposure adjusted incidence rates by treatment group will also be produced for Common (>5%) AEs for two periods – pre COVID-19 pandemic and during COVID-19 pandemic.

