10.4.1.4. Treatment States for AE Data

Non-serious AEs and serious AEs are to be recorded on the eCRF starting at the placebo run-in phase. Serious AEs assessed as related to study procedures or related to a GSK concomitant medication are to be recorded on the eCRF from the time a subject consents

200807

to participation in the study. AE of worsening of an on-going event will be counted once in a particular treatment state.

Treatment State	Definition
Pre-treatment	 For subjects with a non-missing screen failure date, if AE onset is on or before the screen failure date: AE Start Date ≤ Screen Failure Date For randomized subjects with a missing treatment start date, all AEs are considered pre-treatment For randomized subjects with a non-missing treatment start date, if AE onset date is before treatment start date: AE Start Date < Treatment Start Date
Placebo Run-In	If AE onset date or AE worsening date is on or after placebo run-in treatment start date & on or before placebo run-in treatment stop date: Placebo Run-in Treatment Start Date \leq AE Start Date \leq Placebo Run-in Treatment Stop Date Placebo Run-in Treatment Start Date \leq AE Worsening Date \leq Placebo Run-in Treatment Stop Date AE worsening during placebo run-in will be defined relative to the maximum intensity of AE prior to placebo run-in start date. AE worsening date is the first date in the placebo run-in period, when AE intensity increased relative to the maximum intensity of the AE prior to placebo run-in start date.
Post- randomization	If AE onset date or AE worsening date is on or after the randomization date Randomization date ≤ AE Start Date Randomization date ≤ AE Worsening Date AE worsening during post-randomization will be defined relative to the maximum intensity of AE prior to randomization date. AE worsening date is the first date in the post-randomization period, when AE intensity
Treatment emergent	increased relative to the maximum intensity of the AE prior to randomization date. If AE onset date or AE worsening date is on or after treatment start date & on or before the last non-zero dose date plus 1 day. Treatment Start Date ≤ AE Start Date ≤ Last Non-Zero Dose Date + 1 day Treatment Start Date ≤ AE Worsening Date ≤ Last Non-Zero Dose Date + 1 day AE worsening during treatment emergent will be defined relative to the maximum intensity of AE prior to randomized treatment start date.

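### The only planned between-arm comparison of AESIs is a crude on-treatment percentage; the person-year rates required by arm carry no between-arm estimate or confidence interval

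*SAP*

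**What the plan says.** SAP section 8.2.4 makes treatment-emergent AESIs the Tier 1 events. The comparison rule is: "Statistical comparisons will be made to compare the number and % of AESIs between the treatment groups, using the CMH chi-square test". A nominal association is declared when the unadjusted two-sided p-value is below 0.05. Section 8.2.4.2 repeats the tiering and adds the effect measure: "treatment emergent AE of special interest are considered Tier 1 events. The relative risk, corresponding two-sided 95% confidence intervals", with two-sided p-values.

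The window for treatment-emergent events is set in section 10.4.1.4: "Treatment Start Date ≤ AE Start Date ≤ Last Non-Zero Dose Date + 1 day".

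Time at risk does appear in the AESI reporting. Section 8.2.4.2 requires it by arm: "Summaries of AESIs will include the number, percentage and rate per 100 person-years of subjects having at least one occurrence". Section 10.6.4.3 defines the patient-years and the incidence rate per 100 patient-years. Section 8.2.4.2 also says: "Cumulative incidence function (CIF) plots may be produced for each AESI summarizing the time to first occurrence of the AESI by treatment group". These plots treat death as a competing risk and are dropped if fewer than 20 subjects in total have the event. Neither the rates nor the plots come with a between-arm estimate, interval or test.

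**The concern.** A percentage of subjects with an event mixes two things: how often the event occurs per unit of time, and how long subjects were watched. The AESI window closes shortly after the last dose, so the arm that stays on treatment longer collects more events at the same underlying rate. Allocation is 1:1 and the study closes on a common event count, so planned follow-up is balanced. The difficulty arises only if stopping treatment or dying differs by arm.

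The SAP leaves that possibility open. It tests time to stopping treatment for rescue, plans Kaplan-Meier plots of discontinuation by arm, and tests MACE, which includes death, for superiority. If daprodustat subjects are on treatment for less time, a real excess rate is harder to flag. If they are on treatment longer, a false signal becomes more likely. The Tier 1 rule is nominal and outside the multiplicity plan, but it is the only rule stated for declaring an AESI association.

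Elsewhere the SAP does make time-based contrasts. For MACE rates in section 7.2.2: "For difference in rates between treatments, the two-sided 95% CI will be constructed with a Normal approximation". For blood pressure exacerbations in section 8.2.2.2, it uses a "negative binomial model with treatment and the prognostic randomization strata as covariates and the logarithm of time on-treatment as an offset variable".

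**Working it through.** **Is a time-based AESI contrast planned anywhere?**

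- Section 10.6.4.3 defines a rate for each arm and no ratio, difference or interval.
- The dot plot in section 8.2.4.2 shows an incidence rate by arm, but the interval beside it is for the relative risk, and no rate-ratio method is given. This is loose wording.
- Section 8.2.9 comes closest: "A summary of exposure adjusted incidence rates over time (see Section 10.6.4) will be produced by treatment group for any treatment emergent AE". It splits rates by COVID-19 period, has no AESI rows and makes no contrast.
- Thromboembolic events and heart-failure hospitalization have Cox models, and blood pressure exacerbations a rate model (section 8.2.2.2). These overlap with some AESIs but are different endpoints. Cancer, retinal, gastric-erosion, cardiomyopathy, pulmonary-hypertension and rheumatoid AESIs have no such backup.

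**How much could it matter?** The SAP gives no AESI rate, sample size or discontinuation figure for this comparison, so there is no plan figure to reproduce. All inputs are assumed: n = 1000 per arm, cap F = 2.5 years, constant AESI hazard l and discontinuation hazard d, independent of each other.

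- Chance of an on-treatment AESI: P = l/(l+d) × (1 − exp(−(l+d)F)).
- Mean treatment time: (1 − exp(−dF))/d.
- Crude test: pooled two-proportion z, two-sided 5%, counting flags in the direction of harm.
- Rate test: log rate ratio with SE = √(1/E1 + 1/E0), where E is the expected number of events per arm.

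Worked case, rhEPO l = 0.05 and d = 0.20, daprodustat hazard ratio 1.3 (l = 0.065) and d = 0.25:

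- P1 = 0.065/0.315 × (1 − exp(−0.7875)) = 0.1125.
- P0 = 0.05/0.25 × (1 − exp(−0.625)) = 0.0929.
- Crude relative risk 1.21. Difference 0.0195, SE 0.0136; (0.0195 − 1.96 × 0.0136)/0.0136 = −0.52, so the flag probability is 30%.
- Rate ratio: SE = √(1/112.5 + 1/92.9) = 0.140; ln(1.3)/0.140 = 1.87; 1.87 − 1.96 = −0.09, so 46%.

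At 5 events per 100 person-years:

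| Discontinuation per year, daprodustat v rhEPO | Mean exposure (years) | Crude RR when true HR = 1 | Flag when HR = 1.3: crude v rate ratio |
|---|---|---|---|
| 0.20 v 0.20 | 1.97 v 1.97 | 1.00 | 47% v 47% |
| 0.22 v 0.20 | 1.92 v 1.97 | 0.98 | 40% v 47% |
| 0.25 v 0.20 | 1.86 v 1.97 | 0.95 | 30% v 46% |
| 0.30 v 0.20 | 1.76 v 1.97 | 0.90 | 17% v 46% |

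A simulation of the third row (6000 runs) gave 31% v 48%, in line with the formulas.

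Rarer events, discontinuation 0.25 v 0.20 and HR 1.3: 10% v 14% at 1 per 100 person-years, and 7% v 9% at 0.5 per 100.

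Opposite direction, discontinuation 0.20 v 0.25 and HR 1: crude relative risk 1.06 and a false flag of harm 5.8% v 2.5% at 5 per 100 person-years; 3.3% v 2.5% at 0.5 per 100.

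**The case against.** The case against is substantial. The observed on-treatment proportion is a legitimate summary, randomization balances planned follow-up, and nothing in the SAP indicates unequal exposure. The by-arm rate per 100 person-years is mandatory, exposure is summarized by arm (section 6.2.6), and discontinuation curves are plotted (section 6.2.2). If exposure diverged, the percentage and the rate would visibly disagree in the same summary, and a reader could form the ratio from counts and person-years. The rule is nominal, follows a tiered framework the SAP cites, and decides no study conclusion. MACE and blood pressure exacerbations are a co-primary time-to-event endpoint and a recurrent count, so their methods do not by themselves dictate how AESIs should be screened. All of this stands. What remains is that no planned output gives the ratio of rates with its uncertainty, and choosing one after seeing unequal exposure would look post hoc.

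A reader might go further and infer that the CMH rule should be replaced by a rate ratio or Cox model. The documents do not support that. The illustration assumes constant hazards and independent stopping, under which the rate ratio is right by construction. A developing AESI may itself prompt discontinuation, which makes on-treatment censoring informative. A Cox model adjusted for dialysis type and five regions may also be unstable when events are few.

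**Conclusion.** The point holds as a limited gap. The only between-arm AESI comparison is a crude percentage over a window tied to treatment duration, while the required person-year rates have no contrast. The comparison is valid when time on treatment is similar, and can depart from the rate ratio in either direction when it is not.

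The size in this trial is unknown. In the assumed scenarios the loss runs from nothing (equal discontinuation), through 30% v 46% at 5 per 100 person-years with discontinuation 0.25 v 0.20, to 17% v 46% with 0.30 v 0.20. For rare AESIs neither test detects much and the difference is small. It would be wrong to infer that the planned AESI analysis is biased in this trial, or that it leaves exposure out altogether: no exposure imbalance is documented, and rates by arm are reported. This is a cheap improvement.

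**What to change.** In sections 8.2.4 and 8.2.4.2, keep the CMH p-value, percentages, relative risk and dot plot. For each of the eight AESI categories add an exposure-adjusted incidence rate ratio (daprodustat v rhEPO) with 95% confidence interval, using the patient-years of section 10.6.4.3, unadjusted or exact when events are sparse. Repeat it for post-randomization AESIs (on and off treatment), for which section 10.6.4.3 already sets the start of patient-years. State before unblinding that an AESI association is interpreted from both measures, with the rate ratio taken into account when time on treatment differs by arm. Tier 2 and its false discovery rate step need no change.

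The cost is SAP wording, one extra table and its repeat. The on-treatment version assumes a constant rate and non-informative censoring; the post-randomization repeat helps to check the latter.
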